7.2 Secondary Outcome Measure

SDS (Sheehan Disability Scale)

The SDS is a clinician-rated assessment of functional impairment [65]. The items indicate degree of impairment in the domains of work/school, social life, and home life, with response options based on an eleven-point scale (0=not at all to 10=extremely), and five verbal tags (not at all, mildly, moderately, markedly, extremely). Per FDA request, for participants who are not able to work for reasons related to PTSD, the functional impairment item will be scored as a 10. The SDS takes 1 to 2 minutes to complete. [66]64].

MP16 Protocol

Amendment 1 Version 1: 03 January 2018

7.3 Safety Measures

C-SSRS (Columbia Suicide Severity Rating Scale)

The C-SSRS is a clinician-administered measure of suicidal behavior devised to detect potential suicidal thoughts or behaviors during a clinical trial [65]. It consists of a Lifetime version and a Since Last Visit version that assess suicidal ideation, ideation intensity, and behavior. The C-SSRS consists of a series of questions, and can be administered during a face-to-face interview or over the telephone. The Lifetime version will only be administered at the initial Screening visit. All subsequent administrations will utilize the Since Last Visit version. Participants who are discontinuing medications to participate in the study will complete the C-SSRS before and after medication washout. The C-SSRS Intensity scale for Lifetime obtained a Cronbach's alpha of 0.93 and 0.94 for the Since Last Visit form, and Last Visit C-SSRS severity scores were positively correlated with the BDI "suicide thoughts" item [66].

7.4 Screening Measures and Reliability

MINI (Mini-International Neuropsychiatric Interview)

This version of the MINI (7.0.2), a structured interview that was first developed in 1998 to be compatible with DSM and International Classification of Disease (ICD) criteria for psychiatric illnesses [67], is now compatible with DSM-5 and will be administered by a member of the Independent Rater Pool to screen for Axis I psychiatric conditions per DSM-5. Each module of the MINI consists of two or three questions where the answer is either "Yes" or "No," and decision-tree logic is used to determine whether to ask additional questions [70]. The MINI takes between 15 and 20 minutes to perform, and addresses major psychiatric disorders. MINI items were highly reliable (interrater reliability between kappa of 0.8 and 0.99, test-retest reliability between 0.6 and 0.9 for all scales save "current mania), and diagnosis via MINI was comparable to that made with the Composite Diagnostic Interview and the SCID [70, 71] Testing on nonpsychiatric samples did not create false positives [67].

SCID-5-PD (Structured Clinical Interview for DSM-5 for Personality Disorders)

The SCID-5-PD will be administered by a blinded IR via telemedicine [72]. Prior to the SCID-5-PD clinical interview, participants will complete a brief self-report questionnaire called the SCID-5 Self-report Personality Questionnaire (SCID-5-SPQ) as a self-report screening tool used to assess for Axis 2 personality disorders. Potential personality disorders that satisfy diagnostic thresholds will be further assessed via clinical interview during the SCID-5-PD. IRs will receive training on administering these measures from a research reliable trainer. Interviews may be recorded in as many instances as necessary to establish reliability of a random selection of interviews for accuracy.

LEC-5 (Life Events Checklist for DSM-5)

The LEC-5 is a 17-item self-report instrument designed to determine the presence of traumatic life events in the assessment and diagnosis of PTSD. It is a companion measure to the PCL-5 and will be used to assess PTSD. The participant indicates whether each event listed has occurred during their lifetime, permitting the possibility of marking multiple events [73].

PCL-5 (PTSD Checklist)

The PCL-5 is a 20-item self-report questionnaire in which respondents indicate the presence and severity of PTSD symptoms, derived from the symptoms of PTSD per DSM-5 [74]. Participants indicate how much distress they have experienced due to symptoms such as "Repeated, disturbing memories, thoughts, or images of a stressful experience from the past," "Trouble remembering important parts of a stressful experience from the past," and "Feeling irritable or having angry outbursts" on a five-point Likert-type scale (1=Not at all to 5=Extremely). A total PCL-5 score of 50 at Screening will be required for initial enrollment.

DDIS (Dissociative Disorders Interview Schedule for DSM-5)

Questions on the DDIS specifically addressing dissociative disorder symptoms (items 117-130) will be asked by an IR during Screening. These questions are part of an intensive interview that includes questions concerning somatic and psychiatric symptoms. The interview is intended to assess and potentially distinguish between dissociative disorders and other disorders and between Dissociative Identity Disorder (DID) and a dissociative disorder not otherwise specified [75]. Owing to overlap with items found between the DDIS and other screening measures, only questions specifically addressing DID will be assessed.

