3.4 Exploratory Objectives

These objectives may be explored to characterize participants receiving MDMA-assisted psychotherapy to support the primary objective:

- 1. Explore the effect of presence of secondary traumatic stressors (LEC-5) on the CAPS-5 Total Severity analyses
- 2. Explore changes within-participants in PTSD symptom clusters of re-experiencing, avoidance, negative alterations in cognition and mood, and hyperarousal, as measured by changes in CAPS-5 subscale scores from Visit 3 (Baseline) to Visit 19 (18 weeks post Baseline)
- 3. Explore the effect of adverse childhood experiences (ACE) on the CAPS-5 Total Severity analyses
- 4. Explore changes in:
 - Dissociative symptoms associated with PTSD (DSP-I)
 - Depression (BDI-II)
 - Chronic pain (CPGS)
 - Quality of life (EQ-5D-5L)
 - Functioning in relation to self and others (IASC)
 - Psychosocial functioning (IPF)
 - Self-compassion (SCS)
 - Alexithymia (TAS-20)
 - Addictive behaviors including: alcohol use (AUDIT), drug use (DUDIT), and nicotine use (SRNU)
 - Eating habits (EAT-26)
 - Workplace productivity (HPQSF)
 - Healthcare utilization (UFEC)

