7.0 Measures and Reliability

The following eligibility, outcome, exploratory, and safety measures will be used in the study, in accordance with Table 6: Time and Events – Study Measures.

Table 4: Protocol Objectives and Assessment Tools

Objectives	Measure	Measure Type	Administration
Eligibility			
Assess Axis 1 psychiatric disorders	MINI	Eligibility	Site
Assess Axis 2 personality disorders	SCID-5-PD	Eligibility	Telemedicine
	with SCID-		(IR)/ self-report
	5-SPQ		measure at Site

Objectives	Measure	Measure Type	Administration
Confirm PTSD diagnosis and severity	PCL-5 with	Eligibility	Site
	LEC-5		
Identify dissociative disorders	DDIS	Eligibility	Site
Primary		T -	1
Assess changes in PTSD symptom severity	CAPS-5	Outcome	Telemedicine
from Visit 3 to Visit 19 compared between			(IR)
groups			
Secondary			
Assess changes in clinician-rated functional	SDS	Outcome	Telemedicine
impairment from Visit 3 to Visit 19			(IR)
compared between groups			
Safety			1
Compare relative incidence of positive or	C-SSRS	Safety	Site
serious ideation and suicidal behavior			
between groups			
Exploratory	GARS 5		m 1
Characterization of CAPS-5 Total Severity	CAPS-5	Outcome	Telemedicine
score at weeks 6, 10, and 18 to explore onset			
of treatment efficacy with a descriptive time			
course plot	CAPS-5	Outcome	Telemedicine
Explore changes in PTSD symptom clusters	CAPS-3	Outcome	Telemedicine
of re-experiencing, avoidance, negative			
alterations in cognition and mood, and hyperarousal as measured by changes in			
CAPS-5 subscale scores			
Assess overall changes in clinician-rated	SDS	Outcome	Site
functional impairment from Visit 3 to Visit	item scores	Outcome	Site
19 compared between groups	item scores		
Assess changes in severity of dissociative	DSP-I	Outcome	Site
symptoms associated with PTSD from Visit 3	-		
to Visit 19 compared between groups			
Explore correlation of dissociative symptoms	DSP-I	Outcome	Site
associated with PTSD with the CAPS-5 Total	CAPS-5		
Severity analyses			
Explore the effect of presence of secondary	LEC-5	Outcome	Site
traumatic stressors during the assessment	CAPS-5		
period as a covariate on the CAPS-5 Total			
Severity analyses			
Explore the effect of adverse childhood	ACE	Outcome	Site
experiences on PTSD treatment outcomes as	CAPS-5		
a covariate on the CAPS-5 Total Severity			
analyses	CARC 5	0.1	TD 1 1' '
Explore changes in PTSD symptom clusters	CAPS-5	Outcome	Telemedicine
of re-experiencing, avoidance, negative			

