	Visit #	Site A	IR Screening	IR V3	V4	V5	V6&7	IR V8	V9	V10	V11&12	IR V13	V14	V15	V16&17	V18	IR V19	V20
Visit Description	~Time to Complete Measure (minutes)	Site Visit	Tele- medicine	Tele- medicine	Site Visit	Exp. Session 1	Int. Sessions 1.1 & 1.2	CAPS-5 T2: Tele- medicine		Exp. Session 2	Int. Sessions 2.1 & 2.2	CAPS-5 T3: Tele- medicine	Int. Session 2.3	Exp. Session 3	Int. Sessions 3.1 & 3.2	Int. Session 3.3	CAPS-5 T4: Outcome: Tele- medicine	Study Termi- nation
CAPS-5	90 (Baseline) 60 (all others)			✓				\				✓					√	
SDS	2			✓				✓				✓					✓	
DSP-I	15			✓				✓				✓					✓	
C-SSRS B	10	✓	✓		✓	√c	✓		✓	√c	✓		✓	√c	√	✓		√
MINI	15		✓															
SCID-5-SPQ	20	✓																
SCID-5-PD	60		✓															
LEC-5	5	✓							✓				√			✓		√
PCL-5	8	✓			✓				✓				✓					✓
DDIS D	5		✓															
ACE	4				✓													
BDI-II	10 (Baseline) 5 (all others)				√													√
CPGS	5				✓													√
EQ-5D-5L	3				✓													✓
IASC	15				✓													✓
IPF	10				✓													√
SCS	6				✓													✓
TAS-20	5				✓													✓
AUDIT	3	✓																√
DUDIT	3	✓																√
SRNU	3				✓													√
EAT-26	6				✓													✓
HPQSF	5				✓													✓
UFEC	3				✓													
~Total Time of Cor Measures (minutes		49	90	107	93	40	10	77	23	40	10	77	23	40	10	15	77	95

^A Ensure that LEC-5 and SCID-5-SPQ results are sent to the Independent Rater who will be conducting the SCID-5-PD ^B First C-SSRS is a Lifetime assessment, other assessments are Since Last Visit

^C Conducted pre- and post-Investigational Product administration, and at phone calls on Days 2 and 7 after Experimental Session

Description The relevant questions (117-130) from the DDIS will be asked by the Independent Rater during the SCID-5-PD assessment. The entire measure will never be administered.

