11.2 Other Significant Events

Significant life events that may occur during the course of the study, including death of a loved one, loss of employment, or other hardship, may have an impact on treatment outcome. The sponsor will capture these life events using the LEC-5 measure. Such events will be entered as Comments in the eCRF and if appropriate, described in the Case Study Report for data outliers, if any.

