14.1.1.3 Exploratory Analyses

One-group pretest-posttest Cohen's *d* effect size will be estimated. Exploratory sub-group analyses may be conducted when possible to evaluate effects and by individual demographic characteristics (e.g. age, gender, ethnicity, index trauma, dissociative subtype of PTSD, presence of secondary traumatic stressors during the assessment period with LEC-5, medication tapering, diagnosis of comorbid depression, diagnosis of comorbid Axis 2 diagnosis, and number of experimental sessions completed). Post-hoc exploratory analyses not described in the protocol or Statistical Analysis Plan may be performed to further examine the study data. These analyses will be clearly identified as such in the final clinical study report.

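### The LEC-5 has only a lifetime recall frame, so the exploratory covariate for new trauma during the study is undefined and open to missed and mistimed events

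*Protocol*

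**What the plan says.** Protocol 7.4, under the screening measures, describes the instrument: "The LEC-5 is a 17-item self-report instrument designed to determine the presence of traumatic life events". Its recall frame is stated once: "The participant indicates whether each event listed has occurred during their lifetime, permitting the possibility of marking multiple events". Table 6 and SAP Table 3 schedule it at Screening, V9, V14, V18 and V20.

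Three places use it to learn what happened on study:

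- Exploratory objective 1 (Protocol 3.4, repeated in SAP 3.4): "Explore the effect of presence of secondary traumatic stressors (LEC-5) on the CAPS-5 Total Severity analyses". Table 4 adds that this is a covariate on the CAPS-5 analysis and concerns the assessment period.
- Protocol 14.1.1.3 lists among its subgroup factors "presence of secondary traumatic stressors during the assessment period with LEC-5".
- Protocol 11.2, on significant life events in the course of the study: "The sponsor will capture these life events using the LEC-5 measure". It continues: "Such events will be entered as Comments in the eCRF and if appropriate, described in the Case Study Report for data outliers, if any".

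SAP 8.7.3 lists further baseline covariates. On-study stressors are not among them, and the SAP gives no derivation for the LEC-5 variable.

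**The concern.** The question asked of the data concerns an interval, and the form that supplies the data concerns a lifetime. For another repeated measure the protocol makes the switch explicit: "First C-SSRS is a Lifetime assessment, other assessments are Since Last Visit" (Table 6, footnote B). Nothing equivalent is written for the LEC-5.

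The event most likely to be hidden is one that resembles the index trauma. Protocol 8.1.1 has staff support completion of the LEC-5 with the PCL-5 so that the index trauma is properly identified, so its event type should already be ticked at Screening. Protocol 11.2 itself accepts that life events may affect outcome. If they are missed or placed on the wrong side of V3 or V19, the exploratory analysis loses information that cannot be reliably recovered after the visit.

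**Working it through.** The documents give no figure on this point, so there is nothing to reproduce. The check has two parts.

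**1. What undated lifetime ticks can show.**

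- Any endorsement at all: every participant has an index trauma, so this indicator would be positive for practically everyone and could not separate participants.
- Change from Screening: this finds the first occurrence of an event type. A repeat of a type already ticked gives no change.
- Lower time limit: Table 6 shows no LEC-5 between Screening and V9. The V4 total of 93 minutes confirms that none was left out there by accident: 10+8+4+10+5+3+15+10+6+5+3+6+5+3 = 93 without it. The Preparatory Period can last up to 11 weeks (Protocol 5.2), so an item first ticked at V9 may predate V3.
- Upper time limit: V20 falls 1 to 9 days after V19 (Table 1). An item first ticked at V20 may postdate the primary CAPS-5.

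**2. An illustration of the missed repeats.** From the documents: 17 items (Protocol 7.4) and at most N = 60 (Protocol 5.1). Assumed, because the documents give no values: k types already ticked at Screening; a new event equally likely to be any of the 17 types; a true share p with a new stressor; no false positives (mistiming is thus ignored); a standardised CAPS-5 difference of 0.8.

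- Chance that a new event appears as a new tick: s = 1 − k/17.
- Number seen: 60 × p × s.
- Factor by which the exposed-versus-unexposed contrast shrinks: (1 − p)/(1 − p·s).
- Power: two-sample normal approximation, two-sided 5%, with the seen group sizes and the shrunken difference.

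For k = 5 and p = 0.2: s = 12/17 = 0.71; seen = 60 × 0.2 × 0.706 = 8.5 of 12; factor = 0.8/(1 − 0.141) = 0.93.

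| k | s | seen of 12 | factor | power |
|---|---|---|---|---|
| 0 (nothing missed) | 1.00 | 12 | 1.00 | 0.70 |
| 1 | 0.94 | 11.3 | 0.99 | 0.67 |
| 3 | 0.82 | 9.9 | 0.96 | 0.60 |
| 5 | 0.71 | 8.5 | 0.93 | 0.52 |
| 8 | 0.53 | 6.4 | 0.90 | 0.40 |
| 11 | 0.35 | 4.2 | 0.86 | 0.28 |

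Over p = 0.1 to 0.3 the factor runs from 0.99 to 0.78. If new events tend to repeat earlier types, s is lower than shown.

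**The case against.** The lifetime sentence sits among the screening measures and describes the instrument in general terms. Protocol 11.2, Table 4 and 14.1.1.3 all make the on-study purpose plain, and the form actually handed out at V9 to V20 is not in the documents. The site may therefore ask the right question. This is fair as to intent, but the intended frame is not written anywhere as an instruction, and the one frame that is written is the wrong one for the purpose.

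There are other routes of capture. Comments under 11.2 could record a repeat, and text from at most 60 participants can be coded. Nine Integrative Sessions and four calls after each Experimental Session offer chances to hear of an event. Exclusion criterion 3, which is rechecked at Enrollment Confirmation, removes people judged likely to be re-exposed to trauma and so should lower the number of events. All of this stands and limits the harm. None of it links those records to the covariate or dates events against V3 and V19.

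A reader might infer that the covariate is wrong, that the objective cannot be answered, or that the analysis is bound to show no effect of new stressors. The documents do not support these. With no derivation given, the covariate is undefined, which is a different fault. First-ever event types remain detectable against Screening. The shrinkage in the illustration is modest over much of the assumed range. Nor can one say that the typical participant has several traumas: they are allowed, but no frequency is given.

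**Conclusion.** The point holds as a gap in specification. The recall frame, the event date and the derivation rule that the on-study stressor variable needs are all absent, and the stated lifetime frame, followed literally, misses repeats and cannot place new events between V3 and V19. The likely result is under-ascertainment and some mistiming. How much cannot be found from the documents: the figures above rest on assumed values of k, p and the effect size, and on events falling evenly over the 17 types.

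The reach is small. Objectives in 3.4 are ones that may be explored, and the subgroup analyses in 14.1.1.3 are optional. The primary CAPS-5, secondary SDS and safety estimates do not use this variable. It is a cheap improvement of minor priority, best made before data collection because the missing information has to be asked for at the visit.

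**What to change.** 1. Protocol 7.4, with a footnote to Table 6 and SAP Table 3: the Screening LEC-5 keeps the lifetime frame. At V9 the participant answers for events since Baseline (V3); at V14, V18 and V20, for events since the last LEC-5.
2. Protocol 11.2: record the date of each endorsed on-study event in a coded eCRF field, as well as in the Comment.
3. SAP 8.7.3: define the stressor indicator as any LEC-5 item with onset after V3 and on or before V19.

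The cost is one recall instruction on four administrations that already take place, one dated eCRF field and one derivation line in the SAP. The drawback is that the repeats depart from the instrument's lifetime form, which the on-study question does not need after Screening.

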7.5 Exploratory Measures

DSP-I (The Dissociative Subtype of PTSD Interview)

The DSP-I is a clinician-administered interview designed by an international team of PTSD researchers to detect and assess severity of the dissociative type of PTSD and recommended for use as an additional or complementary measure ("add-on") to the CAPS-5 [76-79]. Assessments of military veterans and civilians support the existence of a dissociative subtype of PTSD that is associated with PTSD severity and derealization and depersonalization. The DSP-I takes approximately 5 to 15 minutes to complete. It consists of two parts, only Part 1 will be administered. Part 1 contains five items addressing depersonalization, four items addressing derealization, and a section that is administered if dissociative episodes are endorsed that assesses duration and perceived cause of episodes (seven items) and observer items (three items) addressing interviewee demeanor, including evidence of dissociation, such as forgetfulness or giving a statement that is bizarre within the context of the interview. If two or more items within this section are endorsed, this indicates the presence of other dissociative symptoms beyond depersonalization and derealization. The DSP-I was first developed in 2016 and revised in 2017.

ACE (Adverse Childhood Experience Questionnaire)

The ACE is a 10-item checklist measure assessing number and types of adverse childhood experiences, including neglect and emotional, physical, and sexual abuse. Respondents are asked if an experience happened "often" and if so, to write "1". The total score reflects the number of

adverse childhood experiences. The measure was first used in the context of a study investigating the relationship between childhood adverse experiences and health outcomes in adulthood [74]. Number of frequent adverse childhood experiences is associated with adverse health outcomes in adulthood, including greater likelihood of heart disease, chronic pain, and poor work performance [75-78]. The scoring method has been used in archival research, finding an association between increased scores and health problems in several generations [83].

BDI-II (Beck Depression Inventory II)

The BDI-II is a revision of the BDI, a 21-item self-report measure [79, 80] that will serve as a measure of depression symptom severity [81]. The BDI-II has been validated, has high internal consistency and good test/re-test reliability, and is not overly sensitive to daily variations in mood. It takes 5 to 10 minutes to complete [81]. Score cutoffs indicate: 0 to 13 minimal depression, 14 to 19 mild depression, 20 to 28 moderate depression, and 29 to 63 severe depression. Initial and subsequent studies report that the BDI-II total score has a reliability coefficient of 0.90 to 0.91 which is related to other measures of depression symptoms [81, 82]. Higher scores indicate more severe depressive symptoms.

CPGS (Chronic Pain Grade Scale)

The CPGS is a seven-item measure of pain. Responses to six of the seven items are made on a 10-point Likert scale, and a response on the other item is the number of days in the past 3 to 6 months when pain prevented the respondent from carrying out everyday activities [89]. Responses to questions are used to attain a rating (grade) for pain from 0 (no pain) to five (high disability, severely limiting). The instrument has three scale scores: pain severity, pain intensity, and pain-related disability. Estimated time to complete is 3 to 5 minutes. The CPGS is a validated scale with high internal consistency (Cronbach's alpha = 0.90) and correlated with other instruments assessing pain [90].

EQ-5D-5L (EuroQol Five Dimensions – Five Levels Questionnaire)

The EQ-5D-5L is a two-part self-report questionnaire assessing health status. It consists of five dimensions; mobility, self-care, usual activities, pain-discomfort and anxiety-depression, and one visual analog scale (VAS). Responses are made on each dimension by checking one of five statement that best reflects their health on the day of measure completion, from the healthiest or fewest problems (e.g., "I have no trouble walking about") to the most trouble (e.g., "I am unable to walk about") [89, 90]. In the second part of the EQ-5D-5L, current degree of health ("your health today") is indicated by marking a 20 cm line marked form one to 100, with 100 considered "the best health you can imagine" and one "the worst health you can imagine." The EQ-5D-5L does not sum responses, but treats each response on a dimension as a scale score, and the VAS is the location of the mark in centimeters. The scale can permit comparison across groups on health profiles, and an index can be derived from matching the five dimension scores and the VAS response with nation-specific datasets and calculator software or statistical software syntax designed for the measure. The EQ-5D-5L began as part of the EuroQoL measure, published in 1990 [93]. The instrument has been validated in populations from eight countries. EQ-5D-5L index scores and VAS scores assessed in people with stroke varied with degree of recovery assessed via long-term observation. EO-5D-5L index scores and VAS scores assessed in people with stroke varied with degree of recovery assessed via long-term observation [92]. The EQ-5D-5L takes about 3 minutes to complete.

IASC (Inventory of Altered Self Capacities)

The IASC is a 63-item self-report measure of difficulties with relationships, identity, and affect regulation [95]. The measure is completed by rating the frequency that an event or experience has occurred in the last 6 months or last month (1=Never to 5=Very often) on a five-point Likert scale. The IASC consists of seven 9-item scales: interpersonal conflicts, idealization-disillusionment, abandonment concerns, identity impairment, susceptibility to influence, affect dysregulation, and tension reduction activities. Subscale scores are summed into raw scale scores. Level of symptomatology is assessed through use of t-scores based upon scale norms. IASC subscales range in reliability from Cronbach's alpha of 0.78 to 0.93. IASC scale scores were correlated with a measure of personality disorders and psychiatric symptoms, and affect dysregulation scale scores were associated with a measure of depression [95].

MP16 Protocol

Amendment 1 Version 1: 03 January 2018

Inventory of Psychosocial Functioning

The IPF will be administered as an exploratory measure at Baseline and 2-Month Follow-up. The IPF is a self-report instrument designed to assess functional impairment across a spectrum of domains [96]. The IPF is an 80-item measure that was developed for use among individuals with PTSD. It assesses current psychosocial functioning across seven domains: romantic relationships, family, work, friendships, parenting, education, and self-care. Responses are made on a six point Likert scale, (1=Never to 6=Always). Domain scores can be computed for each subscale, which possess positive correlations with similar scales or subscales on other measures. The IPF has excellent psychometric properties, with Cronbach's alpha for the total scale computed at 0.93 and good internal consistency for subscales (ranging from 0.80 to 0.90) [97].

SCS (Self-Compassion Scale)

The SCS is a 26-item self-report measure of self-compassion, or responding to one's own failure, suffering or inadequacies with kindness and compassion and recognizing one's own flaws and suffering as part of common human experience [98]. Respondents complete the SCS by indicating how typical they feel on each item on a five-point Likert scale (1=Almost never and 5=Almost always). It is estimated to take between 4 to 8 minutes to complete. The scale has six sub-scales: Self-Kindness, Self-Judgment, Common Humanity, Isolation, Mindfulness, and Over-Identified. The mean of subscale scores serves as a total score. Analysis of SCS response indicated that subscales are all related to a higher order factor of self-compassion, and the measure has high test-test reliability at a level of 0.93. Neff *et al.* reported an inverse relationship between SCS total scores and scores on measures of depression and anxiety. Self-compassion and global self-esteem are both related to positive mood and optimism, but self-compassion may be more strongly associated with stable mood and less associated with self-rumination and anger [99].

TAS-20 (Toronto Alexithymia Scale)

The TAS-20 is a 20-item measure of self-reported difficulties with recognizing and verbalizing emotions [101, 102]. Responses are made on a 5-point Likert scale (1=Strongly disagree to 5=Strongly agree). Estimated time of measurement is 5 to 8 minutes. The scale is comprised of three subscales: Difficulty Describing Feelings, Difficulty Identifying Feelings and Externally-Oriented Thinking, with all scales summed to create a total score reflecting presence and degree of alexithymia. The TAS-20 is an established measure and can be used diagnostically with a score of 61 or higher indicative of alexithymia. The TAS-20 is reliable and has good test-retest reliability (Cronbach's alpha of 0.81, test-retest of 0.77).

AUDIT (Alcohol Use Disorders Identification Test)

The AUDIT is a ten-item self-report test. Respondents answer on a 5-point scale (0=Never or none, 4=Daily or greatest number) [102]. The ninth item addresses occurrence of injury of self or other as a result of drinking and the tenth addresses others' concerns about the respondent's drinking, with only three responses provided (0=No, 2=Yes, but not during the last year, 3=Yes, during the last year). The measure can readily detect alcohol abuse disorders in a wide array of individuals [103].

MP16 Protocol

Amendment 1 Version 1: 03 January 2018

DUDIT (Drug Use Disorders Identification Test)

The DUDIT is an 11-item measure designed to assess presence of substance use disorders [105]. Responses to items are made on a 5-point scale with exact responses varying across questions. When present, use can be described in monthly or less than monthly versus four times a week or daily. A list of substances is provided at the end of the measure. The DUDIT is reliable, with a Cronbach's alpha of 0.80. When compared with an interview based on ICD 10, the DUDIT had a sensitivity to detecting substance use disorders of 90% and a specificity of 80% [105]. The English translation was developed from a Swedish-language original. Estimated time to complete is 2 to 4 minutes.

SRNU (Self-reported Nicotine Use)

The SRNU is a sponsor-developed measure that will assess participant's use of nicotine, including approximate frequency of use in the last month and attitudes towards quitting. The measure will take less than 3 minutes to complete.

EAT-26 (Eating Attitudes Test)

The EAT-26 is a 26-item self-report measure that assesses attitudes about eating and food and is used to assess presence of eating disorders. Responses are made on a six-point scale (1=Always to 6=Never), and gathers information on gender, age, height, and weight. The EAT-26 produces a total score and can be used to generate a "referral score." The 27th item addresses the occurrence and frequency of specific eating behaviors, such as binge eating. Estimated time to complete is 4 to 8 minutes. Items on the EAT-26 have high reliability coefficients (Cronbach alpha of 0.83 to 0.90) and has concurrent validity [105].

HPQSF (Health and Work Performance Absenteeism and Presenteeism Short Form)

The HPQSF is a short form of a larger measure of health and work performance that has selected items referring to absenteeism and work performance [106]. The larger measure was created by the WHO as part of the Global Burden of Disease initiative. It consists of eight questions selected from the larger Health and Work Performance Questionnaire, with one question containing five additional items. Items include questions concerning hours worked during an average week, number of whole and partial days missed during a 4-week period, and items that rate average coworker and self-work performance on a ten-point Likert scale (1=Worst performance to 10=Top performance). Hours spent in work over a 4-week period and over the last 7 days can be used to estimate absenteeism, and the HPQSF can also score presenteeism, a measure of actual performance in relation to possible performance. Self-reports on measure appear to match employer records of presence or absence [107], and the HPQSF appears to be reliable between one time point and another (reliability of 0.52) and is sensitive to change [106].

UFEC (Utilization of Facility-based and Emergent Care)

The UFEC is a sponsor-developed measure assessing participant health events, including hospitalization and use of healthcare facilities, including in-patient hospitalization, rehabilitation facilities and other health care facilities for a set period prior to study entry.

MP16 Protocol

Amendment 1 Version 1: 03 January 2018

